10.4 Procedures for Unmasking (if applicable)

All subjects, investigators, and study personnel involved with the conduct of the study will be masked with regard to study drug treatment assignments. When medically necessary, the investigator may need to determine what treatment has been assigned to a subject. When possible (i.e., in non-emergent situations), Ora and/or the Sponsor should be notified before unmasking IP. Ora and/or the study Sponsor must be informed immediately about any unmasking event.

If an investigator identifies a medical need for unmasking the treatment assignment of a subject, he/she should contact Ora and/or the medical monitor prior to unmasking the identity of the IP, if possible. Ora will ask the site to complete and send them the Unmasking Request Form. Ora will notify Aldeyra and jointly will determine if the unmasking request should be granted. They may consult the medical monitor as needed. The result of the request will be documented on the Unmasking Request Form. If approval is granted to unmask a subject, written permission via the Unmasking Request Form will be provided to the investigator. The investigator will unmask the subject using IWRS. The investigator will complete the Unmasking Memo form and include it in the subject's study file and provide a copy for the TMF. For each unmasked request, the reason, date, signature, and name of the person who unmasked the subject, must be noted in the subject's study file.

Unmasked subjects will be discontinued from the study.

10.5 Type and Duration of the Follow-up of Subjects after Adverse Events

The investigator will follow unresolved AEs to resolution until the subject is lost to follow-up or until the AE is otherwise classified. Resolution means the subject has returned to baseline state of health or the investigator does not expect any further improvement or worsening of the AE. If the subject is lost to follow-up, the investigator should make three reasonable attempts to contact the subject via telephone, post, or certified mail. All follow-up will be documented in the subject's source document. Non-

serious AEs identified on the last scheduled contact must be recorded on the AE eCRF with the status noted.

If the investigator becomes aware of any new information regarding an existing SAE (i.e., resolution, change in condition, or new treatment), a new SAE/Unanticipated Report Form must be completed and faxed to Ora within 24 hours of the site's awareness of the new information. The original SAE form is not to be altered. The report should describe whether the event has resolved or continues and how the event was treated.

11 STATISTICAL HYPOTHESES AND METHODS OF ANALYSES

11.1 Analysis Populations

The following analysis populations will be considered:

- Intent-to-Treat Population – The intent-to-treat (ITT) population includes all randomized subjects. Subjects in the ITT population will be analyzed as randomized.
- Per-Protocol Population – The per-protocol (PP) population includes subjects in the ITT population who do not have significant protocol deviations and who complete the study. Protocol deviations will be assessed prior to database lock and unmasking. Subjects in the PP population will be analyzed as treated.
- Safety Population – The safety population includes all randomized subjects who have received at least one dose of the investigational product. Subjects in the safety population will be analyzed as treated.

The primary analysis of ocular dryness score [REDACTED] will be performed on [REDACTED]. The population used for analysis of fluorescein nasal region score will be performed on ITTFSN. The population used for analysis [REDACTED]

[REDACTED] will be performed on ITTOD. The analysis of other secondary efficacy endpoints (except ocular dryness and fluorescein nasal) will be performed for the ITT population and on the PP population as sensitivity analyses. The statistical analysis of safety data will be performed for the safety population.

11.2 Statistical Hypotheses

The following hypothesis will be tested comparing reproxalap to vehicle at 12 weeks. The null hypotheses must be rejected for the dosing regimen to claim efficacy.

11.3 Sample Size

Based on the results of a Phase 2b clinical trial of reproxalap in dry eye disease subjects (ADX-102-DED-009), for the outcome measurements of ocular dryness VAS score and nasal fluorescein staining, approximately 100 subjects per randomized arm will be evaluated in ADX-102-DED-013. Sample size estimates were made assuming an alpha of 0.05 and power of 90% for the two efficacy populations, one with baseline staining severity of 2 units or more and the other with dryness score severity of 3 units or more. Using PASS (software version 14, NCSS, LLC), the sample size estimated for staining was 39 per treatment arm (78 total); the sample size estimated for dryness score was 54 per treatment arm (108 total).

11.4 Statistical Analysis

11.4.1 General Considerations

Quantitative variables will be summarized descriptively using number of subjects (n), mean, standard deviation, median, minimum, and maximum. Qualitative variables will be summarized using counts and percentages.

All summaries will be presented by treatment group. Summaries will be provided for demographics, baseline medical history, concurrent therapies, and subject disposition.

For the purpose of summarization, medical history, concurrent therapies, and adverse events will be coded to MedDRA and WHO Drug dictionaries, as appropriate.

Baseline measures are defined as the last non-missing measure prior to the initiation of randomized study treatment at Day 1. Change from baseline will be calculated as follow-up visit value minus baseline value. Treatment comparisons between active and vehicle will be matched by dosing regimen and calculated as active minus vehicle.

All analyses will be 2-sided at a significance level of 0.05. 95% confidence intervals will be provided where appropriate.

The statistical analysis plan (SAP) will serve as the final determinant of the statistical procedures, notwithstanding anything herein.

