5 OVERALL STUDY DESIGN

The clinical trial is a Phase 2, multicenter, randomized, double-masked, parallel-group, vehicle-controlled design with block enrollment. Subjects will be randomized to one of the following treatment groups at Visit 2 and will be instructed to follow a dosing regimen QID dosing for four weeks followed by BID dosing for weeks 5-12:

- Reproxalap Ophthalmic Solution (0.25% Novel Formulation)
- Vehicle Ophthalmic Solution (vehicle)

[figure not shown]
Approximately 200 subjects will be randomly assigned to one of the two treatment groups (1:1) to receive either Reproxalap Ophthalmic Solution (0.25% Novel Formulation) or vehicle solution as topical ophthalmic drops administered bilaterally QID for four weeks followed by BID dosing for weeks 5-12. Subjects, Sponsor, CRO and site personnel will be masked to treatment assignment.

[figure not shown]
During the screening period, two 90-minute exposures to the CAE® will be conducted to ascertain eligibility to enter the study. Those who qualify will be randomized to receive study drug in a double-masked fashion for 84 days. Subjects will self-administer drops daily as instructed.

At Visits 3 - 9, no CAE® exposure will occur but signs and symptoms will be assessed.

All subjects will dose with randomized treatment QID between Visit 2 and Visit 5 and switch to BID dosing between Visit 5 and Visit 9.

The total number of expected participants, including screen failures, is approximately 500 subjects.

Subjects who terminate early during the treatment period will be asked to complete safety assessments prior to commencement of alternative DED therapy (if possible). Subjects who are terminated early from the study will not be replaced.

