6.3 Inclusion Criteria

Each subject must:

1. Be at least 18 years of age of either gender and any race;
2. Provide written informed consent and sign the Health Information Portability and Accountability Act (HIPAA) form;
3. Have a reported history of dry eye for at least 6 months prior to Visit 1;
4. Have a history of use or desire to use eye drops for dry eye symptoms within 6 months of Visit 1;
5. Report a score of [REDACTED] Questionnaire in at least one symptom at Visit 1 and Visit 2 Pre-CAE®;
6. Have a Schirmer's Test [REDACTED] Visit 1 and Visit 2;
7. Have a tear film break-up time (TFBUT) [REDACTED] Visit 1 and Visit 2 [REDACTED]
8. Have a corneal fluorescein staining [REDACTED] in at least one region (e.g., inferior, superior, or central) at Visit 1 and Visit 2 [REDACTED]
9. Have a sum corneal fluorescein staining score [REDACTED] based on the sum of the inferior, superior, and central regions, at Visit 1 and Visit 2 [REDACTED];
10. Have a total lissamine green conjunctival score [REDACTED] based on the sum of the temporal and nasal regions at Visit 1 and Visit 2 [REDACTED]
11. Demonstrate a response [REDACTED] at Visits 1 and 2 as defined by:

A. Having [REDACTED] in fluorescein staining in the inferior region in at least one eye [REDACTED];

B. Reporting an [REDACTED]

[REDACTED]

13. Have at least one of the following at Visit 2 [REDACTED]

A. [REDACTED]

B. Have a fluorescein staining [REDACTED] in the nasal region in at least one qualifying eye.

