9.3 Examination Procedures

9.3.1 Procedures to be Performed at Each Study Visit with Regard to Study Objective(s)

Procedures listed below should be performed in the given order. See Appendix 2 on methodologies and grading systems.

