9.3.2 Visit 1: Day -14 ± 2 – [REDACTED]

All subjects will undergo the following screening assessments:

[REDACTED]
[REDACTED] Consent/HIPAA

- Demographic Data and Medical/Medication/Ocular History
- Review of Inclusion/Exclusion Criteria
- Urine Pregnancy Test (for females of childbearing potential): Women of childbearing potential must have a negative urine pregnancy test to continue in the study
- Multi-symptom Visual Analogue Scale (VAS)
- [REDACTED]
- [REDACTED]
- [REDACTED]
- [REDACTED]
- BCVA Utilizing an ETDRS Chart
- Slit Lamp Biomicroscopy
- [REDACTED]
- Fluorescein Staining (corneal and conjunctival)
- Lissamine Green Staining (corneal and conjunctival)

[figure not shown]
[REDACTED]

- [REDACTED]
- [REDACTED]
- [REDACTED]
- Slit Lamp Biomicroscopy
- [REDACTED]
- IOP
- Dilated Fundoscopy
- Review of Inclusion/Exclusion Criteria
- Run-in Instillation at the Study Site: All subjects having a positive response (as defined above) and meeting all other screening eligibility criteria at the end of Visit 1 will receive run-in drops for dosing. Qualified subjects will self-administer their initial run-in dose bilaterally at the study site under the supervision of a trained technician.
- Run-in Dispensation: Prior to discharge from the study site on Day -14, subjects will be dispensed sufficient Run-in supply to last until Visit 2 and will be educated on self-administration of vehicle run-in. Subjects will be instructed to self-administer one drop QID in each eye until Visit 2. Subjects will be instructed NOT to instill run-in on the morning of their next scheduled study visit (Visit 2).
- AE Query
- Subjects will be scheduled for Visit 2.

[figure not shown]

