9.3.3 Visit 2: Day 1 – [REDACTED] Confirmation and Baseline

- [REDACTED]
- Study Run-in Collection
- Review of Inclusion/Exclusion Criteria
- Medical/medication history update
- AE query
- Multi-symptom Visual Analogue Scale (VAS)
- [REDACTED]

- [REDACTED]
- [REDACTED]
- [REDACTED]
- BCVA Utilizing an ETDRS Chart
- Slit Lamp Biomicroscopy

- At least 15-minute wait between lissamine green staining and Schirmer's test
- [REDACTED]
- [REDACTED]
- [REDACTED] every 5 minutes thereafter;

- Slit Lamp Biomicroscopy
- Review of Inclusion/Exclusion Criteria
- Randomization
- Study Drug Instillation at the Study Site: All subjects having a positive response (as defined above) and meeting all other screening eligibility criteria at the end of Visit 2 will be randomized to one of two treatment groups utilizing the IWRS system. Randomized subjects will self-administer their initial study drug dose bilaterally at the study site under supervision of a trained technician. Subjects will be instructed to dose four times a day (QID) in both eyes until their next visit.
- Study Drug Dispensation: Prior to discharge from the study site on Visit 2 (Day 1), randomized subjects will be educated on self-administration of study drug. Subjects

will receive their assigned study drug kit with sufficient supply to last until Visit 3 and will be instructed NOT to self-administer study drug on the morning of their next scheduled study visit (Visit 3).

- AE Query
- Subjects will be scheduled for Visit 3.

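### The protocol's baseline rule does not say pre- or post-CAE, so at Visit 2 it picks the second slit-lamp exam, probably post-CAE, to compare with follow-up exams that have no CAE

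*Protocol*

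**What the plan says.** The rule is in Protocol 11.4.1: "Baseline measures are defined as the last non-missing measure prior to the initiation of randomized study treatment at Day 1". Change is the follow-up value minus that baseline. The rule does not mention the CAE.

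Section 5 places the CAE in screening: "two 90-minute exposures to the CAE® will be conducted to ascertain eligibility". It then rules it out for follow-up: "At Visits 3 - 9, no CAE® exposure will occur but signs and symptoms will be assessed".

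Section 9.3.1 fixes the sequence within a visit: "Procedures listed below should be performed in the given order". The visit lists in 9.3.2 to 9.3.10 show the entry "Slit Lamp Biomicroscopy" twice at Visit 1, twice at Visit 2, and once at each of Visits 3 to 9.

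Section 11.4.9 includes slit lamp among the safety endpoints summarized by arm and visit. Changes or shifts from baseline are added where suitable.

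Elsewhere the protocol does separate pre-CAE from post-CAE values. Inclusion criterion 5 in section 6.3 reads in part "Questionnaire in at least one symptom at Visit 1 and Visit 2 Pre-CAE", and section 9.1.5 stratifies on the pre-CAE nasal staining score, which it labels as the Visit 2 baseline.

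Protocol 11.4.1 also gives the SAP the last word on statistical procedures, and SAP section 1 says that its methods replace those of the protocol. SAP 8.3 is the baseline definition. Its first three words match the protocol rule and the rest is redacted. SAP 15.3, on slit lamp, is largely redacted.

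**The concern.** A change from baseline is easiest to read when both values are taken under the same conditions. A 90-minute exposure to an adverse environment is meant to provoke the eye. If the exam that follows it becomes the baseline, each follow-up exam, taken without provocation, is compared with a provoked state.

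What is at stake is how descriptive safety summaries read within each arm. If the CAE worsens a slit-lamp finding, a later worsening on treatment may appear as no change, and a return to the usual state may appear as improvement.

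**Working it through.** This is a check of text and order. The plan gives no figure to reproduce on this point.

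**Step 1: which exam the rule selects.** The relevant visible entries at Visit 2 (Protocol 9.3.3), in the listed order, are:

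1. Dryness and other symptoms on the visual analogue scale (VAS)
2. Visual acuity (BCVA)
3. Slit lamp, first exam
4. "At least 15-minute wait between lissamine green staining" and Schirmer's test
5. A partly redacted entry ending "every 5 minutes thereafter"
6. Slit lamp, second exam
7. Eligibility review
8. Randomization
9. First dose of randomized drug

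Both exams precede the first dose. The last non-missing value before it is the second exam, unless that exam is missing.

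**Step 2: whether the second exam is post-CAE.** The CAE line at Visit 2 is redacted, so this is an inference. The visible support is:

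- Section 5 gives two CAE exposures in screening, and criterion 5 refers to pre-CAE values at Visits 1 and 2.
- Repeated five-minute assessments are listed between the two Visit 2 exams.
- Section 9.3.3 randomizes subjects with a positive response at the end of Visit 2, which fits a challenge completed before randomization.
- The second exam appears only at the visits with a CAE:

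| Visits | CAE | Visible slit-lamp exams per visit | Total |
|---|---|---|---|
| 1 and 2 | Yes | 2 | 2 × 2 = 4 |
| 3 to 9 | No | 1 | 7 × 1 = 7 |
| All nine | | | 11 |

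A second exam is listed at 2 of 2 CAE visits and 0 of 7 visits without CAE.

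**Step 3: which Visit 2 exam matches follow-up.** At all nine visits a slit-lamp exam comes directly after visual acuity. At Visit 2 that is the first exam. The rule therefore uses the unmatched exam for all 7 follow-up visits.

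**Step 4: what follows for the summaries.** Suppose a finding is scored numerically with higher values worse. Let D be a subject's post-CAE value minus the pre-CAE value at Visit 2. Then:

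change from post-CAE baseline = change from pre-CAE baseline − D

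If D is above zero, a true worsening of D or less reads as no change or improvement. If D is zero, the choice of exam makes no difference. If findings are categorical, subtraction does not apply. A shift table is still affected when the CAE moves a subject from normal to abnormal, because an abnormal finding at follow-up is then not counted as a new shift.

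**Step 5: between arms.** D arises before randomization, so its expected value is the same in both arms and cancels from the difference in mean change.

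**Step 6: other measures.** Criterion 11A bases the response required at Visits 1 and 2 on inferior fluorescein staining. This implies that the inferior region is regraded after the CAE. If so, the rule would take the regraded value as baseline.

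**The case against.** The strongest objection is that the governing text cannot be read. The SAP overrides the protocol, and its baseline definition and slit-lamp section are redacted. Either may already name the pre-CAE value. This stands, and it confines the point to the visible protocol rule. No error in the governing analysis is shown, and a redaction is not an omission. The opening words of SAP 8.3 match the protocol rule, which makes a repeat of that rule plausible but does not establish it.

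Second, no visible text says that the CAE changes slit-lamp findings, and the grading scale is redacted. This also stands. The harm is conditional, and the subtraction in step 4 needs a numeric scale and a D above zero. What remains is that the two conditions differ, and that a categorical shift table would not remove the problem if the CAE produces a finding.

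Third, taking the last exam before the first dose is a common safety convention, slit lamp is only summarized descriptively, a subject listing is planned, and the vehicle arm shares the rule. These features limit the consequence. They do not make the two values comparable within an arm.

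Fourth, the counts cover visible lines only. Redacted entries, and the appendices not available here, could add detail.

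A reader might go further and infer that the primary dryness analysis or the nasal staining analyses use a provoked baseline. The documents do not support that. The VAS is visibly listed once at Visit 2, before the serial assessments. No nasal regrading is visible, and section 9.1.5 already ties the baseline nasal score to the pre-CAE value. Nor do the documents support a claim of bias in the comparison of mean change between arms, for the reason in step 5.

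**Conclusion.** The point holds as a minor, free improvement. Followed in the required order, the visible protocol rule makes the second Visit 2 slit-lamp exam the baseline for all 7 follow-up visits, while each follow-up exam corresponds to the first.

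This rests on two assumptions: that the second exam follows the CAE, which is strongly implied but redacted, and that the SAP does not already say otherwise, which cannot be checked here. The size and direction of any distortion cannot be computed, because neither the slit-lamp scale nor any CAE effect on slit lamp is given. The reach is descriptive slit-lamp changes or shifts and, by inference from criterion 11A, change in inferior staining.

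**What to change.** Add one sentence to the baseline definition in SAP 8.3, and align Protocol 11.4.1 at the next amendment: *For any measure taken both before and after the CAE at Visit 2, baseline is the last non-missing pre-CAE value.* This agrees with how section 9.1.5 already treats nasal staining. Use that value in change scores and shift tables, and report the post-CAE slit-lamp exam as a separate Visit 2 time point. If SAP 8.3 and 15.3 already say this, only the protocol sentence needs aligning.

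The cost is one sentence, a check of two SAP sections, and one extra time point in the slit-lamp summary. The first Visit 2 exam is already collected, so no procedure or data collection changes.

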11.4.2 Unit of Analysis

Safety endpoints will be analyzed for both eyes. For efficacy endpoints, the unit of analysis will be the study eye, or the “worst eye,” as defined by the following:

[REDACTED]

11.4.3 Missing Data

The primary analyses using MMRM method will be performed on the ITTOD and ITTFSN population with observed data only. Efficacy analyses may also be conducted using the ITT, ITTOD, and ITTFSN populations with multiple imputation under missing at random (MAR) and missing not at random (MNAR) assumptions. Per-protocol population analysis may also be conducted to assess sensitivity. Further detail will be described in the SAP.

11.4.4 Multiplicity Considerations

A sequential (closed) testing procedure will be used to control the overall Type I error rate due to multiple comparisons for the primary, key secondary and secondary endpoint of fluorescein nasal staining score. The order of treatment comparisons is as follows:

[REDACTED]

11.4.5 Primary Efficacy Analysis

The overall mean change from baseline in [REDACTED] from Week 2 to Week 12 will be analyzed using [REDACTED] in subjects in the ITTOD population.

The [REDACTED] will be fit with baseline value, treatment and visit, as well as the two-way interaction between treatment and visit. Change from baseline of the variable of interest (either ocular dryness or fluorescein nasal staining) will be the dependent variable.

An unstructured covariance structure will be used to model the within-patient correlation over time. The Kenward-Roger approximation will be used to estimate the denominator degrees of freedom. If the unstructured covariance structure matrix results in a lack of convergence under the default fitting algorithm used by PROC MIXED, the model will be fit using covariance matrices of the following order until convergence is met:

- Heterogeneous Toeplitz
- Heterogeneous First-order autoregressive
- Toeplitz
- First-order autoregressive

All the data from the two treatment groups will be included in the models. Comparisons between two treatment groups (for example, between reproxalap and vehicle) at a given visit or for combined visits will be obtained by comparing the corresponding least squares means via customized SAS statements in the model.

Change from baseline will also be analyzed using ANCOVA models with terms for baseline value and treatment group, two-sample t-tests, and Wilcoxon rank sum tests as sensitivity analyses.

[REDACTED]

[REDACTED]
[REDACTED]
[REDACTED]
[REDACTED]

[REDACTED]

- [REDACTED]
[REDACTED]
[REDACTED]
- [REDACTED]
[REDACTED]
[REDACTED]
[REDACTED]

Further details of the analysis plan will be described in statistical analysis plan document (SAP).

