9.1.4 Procedures for Final Study Entry

Subjects must meet all inclusion and none of the exclusion criteria.

9.1.5 Methods for Assignment to Treatment Groups:

Before the initiation of study run-in at Visit 1, each subject who provides written and informed consent will be assigned to a screening number. All screening numbers will be assigned in strict numerical sequence at a site and no numbers will be skipped or omitted. Each subject who meets all the inclusion and none of the exclusion criteria at Visit 1 and Visit 2 will be assigned a randomization number at the end of Visit 2. The Interactive Web Response System (IWRS) will be used to assign all randomization numbers.

Subjects are to be stratified by Visit 2 (Baseline) [REDACTED] and Visit 2 (Baseline) Pre-CAE fluorescein nasal staining score in the study (worst) eye using the following strata:

- [REDACTED]
- [REDACTED]
- [REDACTED]
- [REDACTED]

[REDACTED] will continue until the sample size for the co-primary analysis described in Section 11.3 has been achieved.

Randomization and kit numbers will be assigned automatically to each subject as they are entered into the IWRS.

The site staff will dispense kit(s) required until the next visit. Both the randomization number and the dispensed study drug kit number(s) will be recorded on the subject's source document and electronic case report form (eCRF). The Sponsor, investigators, and study staff will be masked during the randomization process and throughout the study.

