NCS	Not Clinically Significant
OD	Oculus Dexter (Right Eye)
OS	Oculus Sinister (Left Eye)
OSDI	Ocular Surface Disease Index

OU	Oculus Uterque (Both Eyes)
PDF	Portable Document Format
PP	Per Protocol
PPOD	Per Protocol Ocular Dryness
PPFSN	Per Protocol Fluorescein Nasal Score
PT	Preferred Term
QID	Quater in Die (Four Times Daily)
RTF	Rich Text Format
SAE	Serious Adverse Event
SANDE	Symptom Assessment in Dry Eye
SAP	Statistical Analysis Plan
SAS	Statistical Analysis Software
SD	Standard Deviation
SDC	Statistics & Data Corporation, Incorporated
SE	Standard Error
SOC	System Organ Class
SOP	Standard Operating Procedure
TEAE	Treatment-Emergent Adverse Event
TFBUT	Tear Film Break-Up Time
TMF	Trial Master File
VA	Visual Acuity
VAS	Visual Analog Scale
WHODrug	World Health Organization Drug Dictionary

1. Introduction

The purpose of this statistical analysis plan (SAP) is to describe the planned analyses and reporting for protocol ADX-102-DED-013, amendment 1 dated 17 December 2019.

This SAP is being written with due consideration of the recommendations outlined in the most recent International Conference on Harmonisation (ICH) E9 Guideline entitled Guidance for Industry: Statistical Principles for Clinical Trials and the most recent ICH E3 Guideline, entitled Guidance for Industry: Structure and Content of Clinical Study Reports.

[figure not shown]
This SAP describes the data that will be analyzed and the subject characteristics, efficacy, and safety assessments that will be evaluated. This SAP provides details of the specific statistical methods that will be used. The statistical analysis methods presented in this document will supersede the statistical analysis methods described in the clinical protocol. If additional analyses are required to supplement the planned analyses described in this SAP, they may be completed and will be identified in the clinical study report.

[figure not shown]
[figure not shown]
2. Study Objectives

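### The readable model for the dryness endpoint leaves out the nasal-staining randomization stratum; confirm that the redacted SAP model includes it, or add it (small gain, almost no cost)

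*Protocol*

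**What the plan says.** **Randomization.** Protocol 9.1.5 stratifies on two Visit 2 factors. One is redacted. The other is "Visit 2 (Baseline) Pre-CAE fluorescein nasal staining score in the study (worst) eye using the following strata". The cut-points are also redacted. The synopsis says stratification is meant to balance treatment within key subgroups.

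**Primary model.** Protocol 11.4.5 says the model "will be fit with baseline value, treatment and visit, as well as the two-way interaction between treatment and visit". The same form serves change in ocular dryness and change in nasal staining.

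**Sensitivity analyses.** These are "ANCOVA models with terms for baseline value and treatment group, two-sample t-tests, and Wilcoxon rank sum tests as sensitivity analyses". No stratum appears here either.

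**Who enters the dryness analysis.** Inclusion criterion 13 in Protocol 6.3 asks for at least one of two conditions at Visit 2. The first is redacted; the second is a staining threshold "in the nasal region in at least one qualifying eye". The dryness analysis uses the ITTOD population, which is selected on baseline dryness.

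**Which document governs.** Protocol 11.4.5 adds: "Further details of the analysis plan will be described in statistical analysis plan document (SAP". Protocol 11.4.1 states: "The statistical analysis plan (SAP) will serve as the final determinant of the statistical procedures, notwithstanding anything herein". SAP section 1 agrees: "The statistical analysis methods presented in this document will supersede the statistical analysis methods described in the clinical protocol". The SAP text on treatment assignment (4.1), the primary analysis (13.1, 13.1.1) and changes from the protocol (16) is redacted.

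**The concern.** A factor used to stratify randomization would normally be in the analysis model. Stratified blocks force the arms to be alike on the factor, which lowers the true variance of the treatment difference. A model without the factor does not credit that reduction. The between-stratum variation stays in the residual, the standard error is too large, and the test is conservative.

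In the staining model, the baseline value already stands in for the nasal-staining stratum. In the dryness model nothing does, unless the redacted text supplies it. The stratum can also vary in the dryness population, because a subject can satisfy criterion 13 without meeting the staining condition.

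At stake is a little precision on the primary endpoint. Validity is not at stake: the estimate is unbiased and type I error is not inflated.

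**Working it through.** **1. Inputs from the documents.** Two-sided alpha 0.05 (Protocol 11.4.1); 90% power, and "the sample size estimated for dryness score was 54 per treatment arm (108 total") (Protocol 11.3); 1:1 allocation, about 100 per arm (Protocol 6.1).

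**2. Inputs that must be assumed.** The documents give no readable effect size, SD, stratum levels, block size or dryness-population size, and no correlation between nasal staining and dryness change. Assumed:
- partial correlation r of the stratum with dryness change, given baseline dryness: 0 to 0.3
- dryness population: n = 54 to 100 per arm
- a two-level stratum, costing 1 df
- one averaged change score standing in for the MMRM contrast over visits.

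**3. Effect implied by 54 per arm.** The plan's figure cannot be reproduced forwards, so the standardized effect d is back-solved from it.
- Normal approximation: d = (1.960 + 1.282) × √(2/54) = 0.624.
- Noncentral t with 106 df and noncentrality d√(n/2), solved for 90% power: d = 0.6296. This value is used below.

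**4. Formulas.** Let k = 1/√(1 − r²), and let c be the two-sided 5% critical value of t.
- Without the stratum, stratified assignment makes the true SE equal to the model SE divided by k. Type I error = 2·P(T > c·k). Power = P(T′ > c·k), where T′ is noncentral t with 2n − 2 df and noncentrality d·k·√(n/2).
- With the stratum, power = P(T′ > c), with the same noncentrality and 2n − 3 df.

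**5. Results at 54 per arm, stratum balanced by the blocks.**

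| r | Model SE too large by | Type I error without | Power without | Power with | Given up (points) |
|---|---|---|---|---|---|
| 0 | 0% | 5.0% | 90.00% | 90.00% | 0 (adding it costs 0.005) |
| 0.1 | 0.5% | 4.9% | 90.11% | 90.28% | 0.17 |
| 0.2 | 2.1% | 4.6% | 90.45% | 91.12% | 0.67 |
| 0.3 | 4.8% | 4.0% | 91.02% | 92.47% | 1.45 |

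Worked line for r = 0.3: k = 1/√0.91 = 1.048, so the model SE is 4.8% too large. The critical value is effectively 1.983 × 1.048 = 2.078, and 2·P(T > 2.078) on 106 df is 4.0%.

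**6. Larger dryness populations.** Power given up, in points:

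| n per arm | r = 0.1 | r = 0.2 | r = 0.3 |
|---|---|---|---|
| 70 | 0.08 | 0.33 | 0.67 |
| 85 | 0.04 | 0.15 | 0.29 |
| 100 | 0.02 | 0.06 | 0.12 |

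**7. If the blocks do not balance the stratum at all within the dryness population.** Type I error without the stratum is then exactly 5.0%. Power without it stays at 90.00% for 54 per arm. For r = 0.1, 0.2 and 0.3 the power given up is at most 0.28, 1.12 and 2.48 points at 54 per arm, and 0.04, 0.15 and 0.31 at 100 per arm.

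**8. Simulation check.** 20,000 trials per setting, 54 per arm, complete data, ANCOVA on the subject mean, blocks of 4. Each cell gives the 50/50 then the 80/20 stratum split:

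| r | Power gain, points (paired SE) | Type I error without, % | Type I error with, % |
|---|---|---|---|
| 0.1 | 0.15 (0.04); 0.18 (0.05) | 5.15; 5.03 | 5.31; 5.23 |
| 0.2 | 0.73 (0.06); 0.76 (0.07) | 4.62; 4.66 | 5.07; 5.03 |
| 0.3 | 1.58 (0.09); 1.36 (0.08) | 3.94; 4.15 | 4.84; 5.08 |

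The Monte Carlo SE of each error rate is about 0.15 points. The simulation agrees with the closed form, and the unequal split does not change the conclusion.

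**The case against.** The strongest reply is that no defect in the governing plan has been shown. The SAP decides, and the parts that would settle the question are blacked out. Protocol 11.4.5 also has redacted blocks after the ANCOVA sentence. Missing text of this kind is not a missing analysis, and an absent rationale means little when the places that might hold it cannot be read. This stands, and it limits the point to a request for confirmation.

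The effect is also small. In every case computed, the model without the stratum still meets the planned 90% power at 54 per arm. At 100 per arm its power is 99.3% to 99.5%. The value of r is assumed, and r = 0 means no benefit. All of this stands too, and it is why the point is minor.

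It does not remove the point. The readable term lists in 11.4.5 look complete, and they omit a factor that 9.1.5 uses to randomize. Adding the term costs almost nothing even if r = 0, and the choice can only be made cleanly before unmasking.

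A last objection is that the same wording could leave the redacted stratification factor out of the staining model. That is possible but cannot be assessed, because the factor cannot be read.

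**Conclusion.** The point holds as a minor item to confirm. On the readable text, the dryness model and its sensitivity ANCOVA do not include the nasal-staining stratum, and no reason is given. Whether the governing SAP model includes it cannot be determined from the public documents.

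If it is absent, the cost is a slightly conservative test. With balance and r from 0 to 0.3, the loss is 0 to 1.45 points of power at 54 per arm and 0 to 0.12 at 100 per arm. The 1.45 needs both the smallest population and the largest r. With no balance at all, the upper limits are 2.48 and 0.31 points.

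These figures rest on the back-solved effect of 0.63 SD, the assumed r, a two-level stratum that varies in the dryness population, and a single averaged score in place of the MMRM. The 54 per arm is not disputed; its inputs are simply not readable.

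**What to change.** 1. Check whether the dryness model in the unredacted SAP (13.1 and 13.1.1) includes the nasal-staining stratum, or whether section 16 explains its absence.
2. If neither is so, then before unmasking add the stratum, or continuous baseline nasal staining, as a fixed effect in the dryness MMRM and the sensitivity ANCOVA. Keep continuous baseline dryness in both. Stating a reason for leaving the stratum out would also settle the point.
3. Make Protocol 11.4.5 and the SAP agree. If the stratum turns out to be constant in the dryness population, the term drops out.

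The cost is one line of model text and code, since the IWRS already holds the stratum. A two-level stratum uses one degree of freedom. If it proves unrelated to dryness change, that costs about 0.005 points of power at 54 per arm and under 0.001 at 100 per arm. More levels would use more degrees of freedom.
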